APPENDIX B. RESPONSIBILITIES OF THE INVESTIGATOR

Protocol M16-763: ABBV-105, Given Alone or in Combination with Upadacitinib (ABBV-599), in Adult Subjects with Active Rheumatoid Arthritis Who Have Completed a Preceding Phase 2 Randomized Controlled Trial

Protocol Date: 06 February 2020

Clinical research studies sponsored by AbbVie are subject to the International Council for Harmonisation of Technical Requirements for Pharmaceuticals for Human Use (ICH) Good Clinical Practices (GCP) and local regulations and guidelines governing the study at the site location. In signing the Investigator Agreement, the investigator is agreeing to the following:

1. Conducting the study in accordance with ICH GCP, the applicable regulatory requirements, current protocol and operations manual, and making changes to a protocol only after notifying AbbVie and the appropriate Institutional Review Board (IRB)/Independent Ethics Committee (IEC), except when necessary to protect the subject from immediate harm.
2. Personally conducting or supervising the described investigation(s).
3. Informing all subjects, or persons used as controls, that the drugs are being used for investigational purposes and complying with the requirements relating to informed consent and ethics committees (e.g., IEC or IRB) review and approval of the protocol and its amendments.
4. Reporting complaints that occur in the course of the investigation(s) to AbbVie.
5. Reading the information in the Investigator's Brochure/safety material provided, including the instructions for use and the potential risks and side effects of the investigational product(s).
6. Informing all associates, colleagues, and employees assisting in the conduct of the study about their obligations in meeting the above commitments.
7. Maintaining adequate and accurate records of the conduct of the study, making those records available for inspection by representatives of AbbVie and/or the appropriate regulatory agency, and retaining all study-related documents until notification from AbbVie.
8. Maintaining records demonstrating that an ethics committee reviewed and approved the initial clinical protocol and all of its amendments.
9. Reporting promptly, all changes in the research activity and all unanticipated problems involving risks to human subjects or others, to the appropriate individuals (e.g., coordinating investigator, institution director) and/or directly to the ethics committees and AbbVie.

APPENDIX D. ACTIVITY SCHEDULE

The following table shows the required activities across the 8 subject encounters. The individual activities are described in detail in the **Operations Manual**.

	LTE Baseline/ Week 12*	Week 18	Week 24	Week 30	Week 36	Week 48	Week 60/PD	Follow-up call (30 days after last dose)
		± 7 days	± 7 days	± 7 days	± 7 days	± 7 days	± 7 days	
Subject information and informed consent	✓							
Eligibility criteria	✓							
Medical and surgical history	✓							
Prior/concomitant therapy	✓*	✓	✓	✓	✓	✓	✓	✓
AE assessment		✓	✓	✓	✓	✓	✓	✓
Patient Questionnaires: 
 • Patient's Assessment of Pain (VAS) • PtGA • HAQ-DI • Morning Stiffness 	✓*	✓	✓	✓	✓	✓	✓	
TJC68/SJC66	✓*	✓	✓	✓	✓	✓	✓	
PhGA	✓*	✓	✓	✓	✓	✓	✓	
12-lead ECG	✓*	✓	✓	✓	✓	✓	✓	
Body weight	✓*	✓	✓	✓	✓	✓	✓	
Vital signs	✓*	✓	✓	✓	✓	✓	✓	
Physical exam	✓*	✓	✓	✓	✓	✓	✓	
Local urine pregnancy test (for all female subjects of childbearing potential)	✓*	✓	✓	✓	✓	✓	✓	
Dispense urine pregnancy tests for monthly home testing	✓	✓	✓	✓	✓	✓		
Local laboratory test - Erythrocyte sedimentation rate (ESR)	✓*	✓	✓	✓	✓	✓	✓	

	LTE Baseline/ Week 12*	Week 18	Week 24	Week 30	Week 36	Week 48	Week 60/PD	Follow-up call (30 days after last dose)
		± 7 days	± 7 days	± 7 days	± 7 days	± 7 days	± 7 days	
Central laboratory tests: 
 Hematology Blood chemistry Urinalysis hsCRP 	✓*	✓	✓	✓	✓	✓	✓	
Central laboratory test - TB screen (QuantiFERON-TB Gold test or interferon gamma release assay [IGRA] equivalent and/or local purified protein derivative [PPD] skin test) or T SPOT®.TB test**						✓		
Optional biomarker sample: Whole blood (serum, plasma, RNA, and DNA)	✓*		✓			✓		
Drug assignment	✓							
Dispense study drug and subject dosing diary	✓*		✓		✓	✓		
Review study drug returned and perform drug reconciliation	✓*	✓	✓	✓	✓	✓	✓	
Reminder to subjects to perform their weekly at-home temperature monitoring***	✓*	✓	✓	✓	✓	✓	✓	

* Tests/study activities are only to be performed if not done as part of Study M16-063.

** As available and if compliant with local TB guidelines (Canada only).

*** As described in Section 6.2.

APPENDIX E. PROTOCOL AMENDMENT SUMMARY OF CHANGES

Previous Protocol Version

Protocol	Date
Version 1.0	06 August 2018
Version 1.1 (Canada Only)	12 October 2018
Version 2.0	12 October 2018
Version 2.1 (VHP)	17 December 2018
Version 3.0	17 January 2019

- Added CDAI efficacy endpoints to Section 3.2.

Rationale: To add endpoints that use a disease activity index that is not influenced by CRP, who's synthesis by the liver is directly blocked by JAK inhibition.
- Added further detail to Eligibility Criterion 2j in Section 5.1.

Rationale: To clarify proper birth control practices that are to be followed during the study.
- Removed "relative to baseline from Study M16-063" from discontinuation criteria around worsening of SJC and/or TJC, subjects failing to achieve at least 20% improvement in SJC and TJC starting at Week 18, and subjects who fail to achieve CDAI \leq 10 starting at Week 18 (Section 5.5).

Rationale: To clarify discontinuation criteria.
- Added further detail to study drug discontinuation instructions in Section 5.6.

Rationale: To ensure study drug discontinuation processes are clear.
- Added clarification to the study drug dispensation instructions in Section 5.7.

Rationale: To ensure that study drug is properly dispensed.
- Added information around the Safety Analysis set to Section 7.2 and Section 7.4.

Rationale: To clarify the Safety Analysis Set parameters.
- Added an All ABBV-599 efficacy analysis set and clarifying language in Section 7.3.

Rationale: To run an efficacy analysis on all subjects who received study drug.
- Added an Interim Analysis (Section 7.5).

Rationale: To explain the planned, unblinded interim analysis that will be conducted after the Study M16-063 Week 12 database lock.
- Removed Troponin and Troponin + CK MB testing from Section 3.11 of the Operations Manual (Protocol Appendix F).

Rationale: Asymptomatic CPK elevation is a known JAK inhibitor class effect and is described in the Rinvoq USPI and SmPC. Testing asymptomatic subjects with more specific tests designed only for those with suspicion for myocardial infarction (CK-MB and troponin is not warranted and may lead to unnecessary cardiac evaluations and patient anxiety).

- Added clarification around which type of herpes zoster vaccine the instructions are referring to in Section 3.11 of the Operations Manual (Protocol [Appendix F](#)).

Rationale: To ensure it's understood that this requirement only applies to those taking a live herpes zoster vaccine.

- Remove reference to liver biopsies from Section 4.1 of the Operations Manual (Protocol [Appendix F](#)).

Rationale: To clarify that there are no liver biopsies at Screening or any time during the Study.

In addition to these modifications, the Amendment contains the following minor changes:

Update Section [2.1](#) to align with current upadacitinib development program.

Update wording in Section [2.1](#) and Section [2.2](#) for clarity.

Update wording in Section [3.3](#) to clarify that separate DMC and CAC charters have been prepared outside of the protocol.

Update wording around study drug discontinuation in Section [6.2](#) for clarity.

Update Sponsor/Emergency Medical Contact throughout.

Update to protocol signatories ([Appendix C](#), List of Protocol Signatories).

Added [Appendix F](#) to align with the updated AbbVie Protocol template.

Update abbreviations throughout for consistency.

APPENDIX F. OPERATIONS MANUAL

## **1.0 Introduction**

This Statistical Analysis Plan (SAP) describes the statistical analyses for ABBV-599 Study M16-763.

Study M16-763 evaluates the long-term safety, tolerability, and efficacy of ABBV-105 and ABBV-599 in RA subjects who have completed Study M16-063.

The SAP will not be updated in case of administrative changes or amendments to the protocol unless the changes impact the analysis.

Unless noted otherwise, all analyses will be performed using SAS Version 9.4 (SAS Institute Inc., Cary, NC 27513) under the UNIX operating system.

## **2.0 Study Design and Objectives**

### **2.1 Objectives and Hypotheses**

The primary objective of this study is to evaluate the long-term safety, tolerability, and efficacy of ABBV-105 and ABBV-599 in RA subjects who have completed Study M16-063.

#### **Clinical Hypothesis**

[figure not shown]
The safety and efficacy of ABBV-105 and ABBV-599 will be maintained over an extended period of treatment.

### **2.2 Study Design Overview**

This is a Phase 2, double-blind, multicenter, long-term extension (LTE) study to assess the safety, tolerability, and efficacy of ABBV-105 and ABBV-599 in RA subjects who have completed Study M16-063.

The schematic of the study is shown in [Figure 1](#).

**Figure 1. Study Schematic**

QD = once daily

### 2.3 Treatment Assignment and Blinding

Subjects who meet eligibility criteria as specified in Section 5.1 of the protocol and enter the study on ABBV-105, ABBV-599, or upadacitinib from Study M16-063 will continue on their previously-assigned treatment through the end of the LTE study. Subjects who meet eligibility criteria and enter the study on placebo for both ABBV-105 and upadacitinib from Study M16-063 will receive ABBV-599. Study drug treatment assignments include the following:

- Group 1: ABBV-599 (ABBV-105 60 mg and upadacitinib 15 mg) administered once a day (QD),
- Group 2: ABBV-105 60 mg and upadacitinib placebo QD,

- Group 3: ABBV-105 20 mg and upadacitinib placebo QD
- Group 4: ABBV-105 5 mg and upadacitinib placebo QD, and
- Group 5: Upadacitinib 15 mg and ABBV-105 placebo QD.

This study plans to enroll subjects who completed Study M16-063 at approximately 39 sites in Canada and the European Union. The number, allocation, and location of sites may vary depending on operational aspects of the study. Study sites and subjects will remain blinded for the duration of the study.

The duration of the LTE study will be approximately 52 weeks. This includes a 48-week double-blind treatment period with study visits conducted at Weeks 18, 24, 30, 36, 48, and 60 from the baseline visit of Study M16-063. In addition, subjects will also have a telephone follow-up call 30 days after their last visit to determine the status of any ongoing AEs/SAEs or the occurrence of any new AEs/SAEs.

## **2.4 Sample Size Determination**

This is the LTE study for Study M16-063. All eligible subjects who completed Study M16-063 will be enrolled in this study if the subject signs and dates the informed consent. Based on discontinuation criteria mandating efficacy, it is estimated that 20 - 60% of subjects (i.e., between 40 and 120 subjects) will ultimately complete the LTE.

## **3.0 Endpoints**

### **3.1 Primary Efficacy Endpoint**

There is no primary efficacy endpoint since this is the extension to the feeder Study M16-063.

### **3.2 Secondary Efficacy Endpoints**

1. Change in disease activity score (DAS)28 (C-reactive protein [CRP]) from baseline of Study M16-063;
2. DAS Low Disease Activity (LDA), defined as DAS28 CRP  $\leq$  3.2;

3. DAS Clinical Remission (CR), defined as DAS28 CRP < 2.6;
4. Change in clinical disease activity index (CDAI) from baseline of Study M16-063;
5. LDA based on CDAI criteria, defined as CDAI  $\leq$  10;
6. CR based on CDAI criteria, defined as CR  $\leq$  2.8;
7. American College of Rheumatology (ACR) 20/50/70 response. A subject will be considered an ACR 20/50/70 responder if:
  - The swollen joint count (SJC) and tender joint count (TJC) have decreased from baseline of Study M16-063 by 20/50/70% or more.
  - At least 3 of the 5 remaining ACR core set measures show reduction of 20/50/70% or more from baseline of Study M16-063.
    - Patient's Assessment of Pain [using visual analog scale, VAS],
    - Patient Global Assessment of Disease Activity [PtGA],
    - Physician Global Assessment of Disease Activity [PhGA],
    - Health Assessment Questionnaire Disability Index [HAQ-DI]
    - High-sensitivity C-reactive protein [hsCRP])
8. Change in individual components of ACR from baseline of Study M16-063, to include:
  - SJC,
  - TJC,
  - Patient's Assessment of Pain (using VAS),
  - PtGA,
  - PhGA,
  - HAQ-DI, and
  - hsCRP.
9. Change in Morning Stiffness Severity (11 point scale) from baseline of Study M16-063.

10. Change in Morning Stiffness Duration (Hours and Minutes) from baseline of Study M16-063

### **3.3 Other Efficacy Endpoints**

The secondary efficacy endpoints are listed in Section 3.2, respectively. There are no additional efficacy endpoints.

### **3.4 Safety Endpoints**

Safety evaluations include adverse event (AE) monitoring, physical examinations, vital sign measurements, electrocardiogram (ECG), and clinical laboratory testing (hematology, chemistry, and urinalysis) as a measure of safety and tolerability for the entire study duration.

An internal independent data monitoring committee (IDMC) will review unblinded safety data on a cohort level throughout the course of the study. A separate IDMC charter will be prepared outside of the protocol and will describe the roles and responsibilities of the IDMC members, frequency of data reviews, relevant safety data to be assessed, and expectations for blinded communications.

An independent Cardiovascular Adjudication Committee (CAC) will adjudicate blinded cardiac and cerebrovascular events. A CAC charter will be prepared separately from the protocol that will define objective, scope, frequency, and triggers of data reviews.

### **3.5 Additional Endpoint(s)**

No additional endpoints will be analyzed in the SAP. Pharmacokinetic endpoints and biomarker endpoints will be analyzed separately.

### **4.0 Analysis Populations**

The following population sets will be used for the analyses.

The Full Analysis Set (FAS) includes all subjects who enrolled in Study M16-763 and received at least 1 dose of assigned study drug. The FAS will be used for efficacy and baseline analyses. Subjects will be grouped according to treatments as randomized for Study M16-063.

The Safety Analysis Set consists of all subjects who enrolled in Study M16-763 and received at least 1 dose of assigned study drug. Subjects will be grouped according to treatments actually received in Study M16-763. The Safety Analysis Set will be used for safety analyses.

## **5.0 Subject Disposition**

The number of subjects will be tabulated by country, investigator site and overall for all enrolled subjects.

The total number of subjects who were enrolled and treated will be summarized.

A summary of subject accountability will be provided where the number of subjects in each of the following categories will be summarized for each treatment group:

- Subjects enrolled in the study;
- Subjects who took at least one dose of study drug;
- Subjects who completed protocol-specified treatment;
- Subjects who prematurely discontinued study drug (all reasons and primary reason);
- Subjects in each analysis population.

In addition, the reasons for premature discontinuation (primary reason and all reasons) from the trial and/or from the medication collected from CRF by the following categories will be summarized with frequencies and percentages. Subjects with multiple reasons for premature discontinuation will be counted once in the calculation of the number and percentage of total discontinuations ("Premature Discontinuation").

- Adverse events,
- Lost to follow-up,
- Withdrew consent by subject,
- Lack of efficacy,
- Other.

## 6.0 Study Drug Duration and Compliance

A summary of study drug duration (days) will be provided by each treatment arm for the Safety Analysis Set.

The duration of exposure to study drug will be summarized by groups as specified below.

- Group 1: ABBV-599 Always
- Group 2: ABBV-105 60 mg
- Group 3: ABBV-105 20 mg
- Group 4: ABBV-105 5 mg
- Group 5: Upadacitinib
- Group 6: ABBV-599 After Placebo
- Group 7: Placebo (Not present in Study M16-763)

The duration of exposure to study drug will be summarized for each group as specified above, with the number of subjects, mean, standard deviation, median, minimum and maximum values. In addition, the number and percentage of subjects exposed to study drug will be summarized for Study M16-063/763 combined and for Study M16-763 treatment period only respectively. For Study M16-063/763 combined, the following duration intervals will be used:

- $\geq 1$  day
- $\geq 15$  days
- $\geq 29$  days

- $\geq 57$  days
- $\geq 85$  days
- $\geq 127$  days
- $\geq 169$  days
- $\geq 211$  days
- $\geq 252$  days
- $\geq 336$  days
- $\geq 420$  days

The exposure to study drug in days for Study M16-063/763 combined period is calculated as:

Exposure = (date of last study medication in Study M16-763 – date of first study medication in Study M16-063 + 1)

For Study M16-763 only, the following duration intervals will be used:

- $\geq 1$  day
- $\geq 42$  days
- $\geq 85$  days
- $\geq 127$  days
- $\geq 168$  days
- $\geq 252$  days
- $\geq 336$  days

The exposure to study drug in days for Study M16-763 period only is calculated as:

Exposure = (date of last study medication in Study M16-763 – date of first study medication in Study M16-763 + 1)

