### **9.2.3 Treatment-Emergent Adverse Events by SOC and/or PT**

The number and percentage of subjects experiencing adverse events will be tabulated by SOC and MedDRA PT by "as treated" treatment groups and overall. The SOCs will be presented in alphabetical order, and the PTs will be presented in alphabetical order within each SOC.

The following summaries of adverse events will be generated:

- All TEAEs
- Treatment-emergent serious adverse events (SAEs)
- Treatment-emergent severe adverse events
- TEAEs reasonably possibly related to study drug
- TEAEs leading to discontinuation of study drug
- TEAE leading to death
- Frequent AEs (reported in 2% of subjects or more in any treatment group)

Subjects reporting more than one adverse event for a given MedDRA preferred term will be counted only once for that term (most severe incident for the severity tables and most related incident for the relationship tables). Subjects reporting more than one type of adverse event within a SOC will be counted only once for that SOC. Subjects reporting more than one type of adverse event will be counted only once in the overall total. In addition, if the same adverse event occurs multiple times within a subject, the highest

severity and level of relationship to investigational product will be reported. In addition, TEAEs will be summarized by PT and sorted by decreasing frequency for the total active group.

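### SAP 6.0 lists separate placebo and ABBV-599-after-placebo groups, but no rule splits the switchers' combined-period exposure and events at the switch

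*SAP*

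**What the plan says.** SAP 2.3 sets the switch: "Subjects who meet eligibility criteria and enter the study on placebo for both ABBV-105 and upadacitinib from Study M16-063 will receive ABBV-599". SAP 6.0 then lists the exposure groups, among them "Group 6: ABBV-599 After Placebo" and "Group 7: Placebo (Not present in Study M16-763"). SAP 9.2.2 uses the same list for the TEAE overview.

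For the two studies combined, SAP 6.0 gives one formula: "Exposure = (date of last study medication in Study M16-763 – date of first study medication in Study M16-063 + 1"). SAP 9.2.1 opens the combined TEAE window at the first M16-063 dose and closes it 30 days after the last M16-763 dose. SAP 4.0 says of the Safety Analysis Set: "Subjects will be grouped according to treatments actually received in Study M16-763".

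SAP 9.2 restricts rates per 100 patient-years to the combined data, and SAP 9.2.4 uses total study drug exposure as their denominator without naming treatment groups. Protocol 7.4 plans such rates for SAEs, deaths, AEs leading to discontinuation and AESI.

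For M16-763 alone, both the exposure formula and the TEAE window start at the first M16-763 dose.

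**The concern.** A placebo group that is absent from M16-763 has a purpose only if the switchers' M16-063 time is reported apart from their ABBV-599 time. The group list therefore points to a split, but the formula, the event window and the grouping rule do not provide one. A programmer who follows the formula puts placebo time in Group 6. One who follows the labels has to invent a cut date and a rule for assigning events.

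Three outputs are at stake:
- **Combined exposure table.** It is presented by these groups, so it is affected directly.
- **Combined TEAE tables.** Those presented by the 6.0 groups are affected in the same way.
- **Rates per 100 patient-years.** They are affected if shown by the 6.0 groups. As only combined data feed them, the plan has no extension-only rate to check them against.

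Long-term safety of ABBV-599 is part of the primary objective, and Group 6 is one of the two groups that supply it.

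**Working it through.** **Inputs**
- Placebo phase: the Protocol Appendix D schedule heads its first column "LTE Baseline/ Week 12", so 12 × 7 = 84 nominal days.
- Extension: SAP 2.3 gives a "48-week double-blind treatment period with study visits conducted at Weeks 18, 24, 30, 36, 48, and 60 from the baseline visit of Study M16-063", so 48 × 7 = 336 nominal days.
- Completion: SAP 2.4 and Protocol 7.3 estimate 20–60%, for the whole study.
- Placebo-to-active event rate ratio k: not in the documents, so k = 0.5, 1 and 2 are assumed.

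Visit windows and day-level offsets are ignored.

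**1. The plan's own figures.** 84 + 336 = 420 days, the top combined-period interval in SAP 6.0. 336 days is its top M16-763-only interval. Both are reproduced.

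**2. One completer who switched.** Put the first M16-063 dose on Day 1, the first M16-763 dose on Day 85 and the last dose on Day 420. The combined formula gives 420 − 1 + 1 = 420 days, all in Group 6. Time on ABBV-599 is 420 − 85 + 1 = 336 days. The placebo share is 84/420 = 20%.

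**3. Group 7.** The formula needs a last M16-763 dose, and nobody takes placebo for both drugs in M16-763. Group 7 thus has no end date under SAP 6.0 and no members under SAP 4.0. Applying the formula to the same subjects would only repeat the Group 6 value.

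**4. Pooled placebo share of Group 6.** A group rate uses pooled person-time, so the distribution of stopping times matters and the number of switchers cancels out. Assume that the completion estimate applies to switchers and that all non-completers stop at one visit. Then s = 12 / mean week of last dose.

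| Completers | Others stop at | Mean week | s |
|---|---|---|---|
| 20% | Week 18 | 0.2 × 60 + 0.8 × 18 = 26.4 | 45% |
| 60% | Week 18 | 0.6 × 60 + 0.4 × 18 = 43.2 | 28% |
| 20% | Week 48 | 0.2 × 60 + 0.8 × 48 = 50.4 | 24% |
| 60% | Week 48 | 0.6 × 60 + 0.4 × 48 = 55.2 | 22% |

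Stops before Week 18 would raise s.

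**5. Effect on a Group 6 rate.** Reported/true = (1 − s) + s × k = 1 − s(1 − k).

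| k | s = 12/55.2 | s = 12/26.4 |
|---|---|---|
| 0.5 | 0.89 | 0.77 |
| 1 | 1.00 | 1.00 |
| 2 | 1.22 | 1.45 |

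**6. Side effect of a cut.** The combined dataset holds only subjects who completed M16-063 and were then dosed in M16-763. Its M16-063 time is therefore free of deaths, and largely free of AEs leading to discontinuation, by selection. Groups 1–5 keep 12 such weeks each; after a cut, Group 6 does not. With equal true extension rates, Group 6 would show a higher rate for these events by the factor mean week / (mean week − 12): 55.2/43.2 = 1.28 to 26.4/14.4 = 1.83.

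**The case against.** The strongest reply is that the group names already settle the matter. SAP 6.0 separates the two groups, several AE sections ask for as-treated groups, and counting placebo time in Group 6 would empty a group that the SAP lists. Nor can SAP 4.0 be meant literally, since grouping only by M16-763 treatment would merge Groups 1 and 6. On this view a sentence is missing and the analysis itself is not wrong. That stands as an account of intent. It supplies no cut date and no event rule, and the one stated formula gives a wrong value for a listed group. Reading study medication as active drug only does not help, because Protocol 5.7 includes matching placebo in study drug.

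The second reply is that rate bias is conditional. That also stands. SAP 9.2.4 and Protocol 7.4 name no groups, so a reader might infer that biased ABBV-599 rates are planned, but the documents do not say so.

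The third concerns size. A single switcher who stops at Week 18 has 84/126 = 67% placebo time, and a reader might take that as the effect on the group. It is an individual extreme; step 4 gives the pooled range.

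A reader might also take the TEAE listing "sorted by decreasing frequency for the total active group" as proof that a placebo group sits beside it. That is weak evidence: every M16-763 group is active, so the phrase may mean all of them.

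Finally, a cut costs some comparability. At present Groups 1–6 all carry the same 84 selected days; step 6 shows what changes for deaths and AEs leading to discontinuation. This calls for a footnote and does not justify leaving placebo time in Group 6.

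**Conclusion.** The point holds and should be fixed. The SAP evidently intends to separate placebo from ABBV-599 time but states no rule, and its combined formula and TEAE window applied as written place both in Group 6 and leave Group 7 uncomputable. The exposure table is affected without further condition: a completer with 336 nominal days on ABBV-599 appears at 420 or more. Combined TEAE tables by the 6.0 groups mix the two periods. Patient-year rates do so only if they follow those groups.

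The 22–45% pooled placebo share rests on applying a study-wide completion estimate to switchers, with other stops between Weeks 18 and 48. The rate factors also need k, which is unknown. A reader might infer that the ABBV-599 rate is understated, but the direction depends on k and there is no bias at k = 1.

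A reader might also infer that the safety analysis as a whole is compromised. It is not: M16-763-only exposure and TEAE percentages are a clean view of Group 6, and Groups 1–5 have no misattribution.

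**What to change.** State one rule for placebo switchers in SAP 4.0, 6.0, 9.2.1 and 9.2.4, and carry it into the SAP 9.3 laboratory summaries that span both studies, where minimum and maximum categories could otherwise mix the two periods:

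- Group 6 exposure and events start at the first M16-763 dose.
- Group 7 exposure is the date of the first M16-763 dose minus the date of the first M16-063 dose. Events with onset before the first M16-763 dose go to Group 7.
- Events on or after that dose, or with an incomplete onset date not shown to precede it, go to Group 6.
- The SAP 9.2.4 rates use these groups, and each switcher counts once in the overall column.
- A footnote says that M16-063 time in this dataset comes from completers only, so Group 6 is not directly comparable with Groups 1–5 on deaths and AEs leading to discontinuation.

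For the completer in step 2 this gives 336 days in Group 6 and 85 − 1 = 84 in Group 7. They add to the present 420, so total patient-years and events do not change.

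The cost is SAP wording and programming. The dose dates already enter the SAP 6.0 formulas, no new data are needed and Protocol 7.4 can stay as it is. Rates on M16-763-only exposure for deaths and AEs leading to discontinuation would be a cheap optional supplement. They would need the SAP 9.2 restriction to combined data relaxed and are not a required part of the correction.
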